### Relationship with Study Device

Treatment-related AE is defined as a AE with a relationship as “Possibly Related”, “Probably Related” or “Definitely Related” or “Unable to Judge” to the study treatment. AEs with a missing relationship to study treatment will be regarded as “Definitely Related” to study treatment. If a patient reports the same AE more than once within that SOC/ PT, the AE with the worst-case relationship to study medication will be used in the corresponding relationship summaries.

### Relationship with study procedure

AEs related to study procedure is defined as a AE with a relationship to the study procedure as “possibly related”, “probably related” or “definitely related” or “unable to judge” to study procedure. If a patient reports the same AE more than once within that SOC/ PT, the AE with the worst-case relationship to study medication will be used in the corresponding relationship summaries.

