For all AEs associated with patients, a full description of the event should be recorded in the eCRF including the date and time of onset (when the signs and symptoms of the event began), outcome, seriousness, severity, event description, actions taken, and causal relationship of the AE or SAE. Investigators should review and reference the severity (refer to Table 2) and causality definitions (refer to Table 3) when determining relationship of the AE or SAE to the study device and procedure. The investigator may also discuss the event(s) with the Sponsor's Medical Monitor or designee.

For all AEs associated with users or other persons (not the study patient), a full description of the event should be recorded on the paper AE form and sent via email to Sponsor designee and Baxter Global Patient Safety Medical Device Vigilance

[REDACTED].

All AEs and SAEs should be actively solicited and documented in the eCRFs, no matter how common they are for a patient and regardless of the causality assigned by the investigator. Additionally, any AE and SAEs voluntarily reported by the patient should be recorded in the eCRF and verified by the investigator or designee with the relevant source documents.

The outcome/resolution of all AEs and SAEs will be determined by the investigator and documented in the eCRF. Investigators will follow all unrelated AEs and SAEs until resolution, stable, or the end of the study, whichever occurs first, and follow all study device-related and procedure-related AEs and SAEs until resolution or stable, including following the patient after the end of the study if necessary. Outcomes and other relevant information obtained after the end of the study will be reported via the paper AE form and sent via email to Baxter Global Patient Safety Medical Device Vigilance [REDACTED].

For the outcome categories that can be used in the eCRF by the investigator refer to Table 4.

During the study period, if a patient experiences an AE which is considered causally related to a Baxter medicinal/drug product (not the study medical device or comparator), the event shall be forwarded by the investigator or designee within 24 hours of becoming aware of the AE to Baxter

Global Patient Safety [REDACTED] for assessment as per Baxter's process for case processing of spontaneous reports.

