## 8 Statistical Considerations

### 8.1 Missing Data

For the primary efficacy endpoints, multiple imputation and tipping point analysis will be used to impute missing values of the  $\lambda$  FLC and  $\beta$ 2-MG RRs using the Intention-to-treat FAS for the sensitivity analysis. Imputation method are detailed in section 17.1.3.

No additional data will be imputed.

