### Relationship with Study Device/ Study Procedure

Relationship, as indicated by the Investigator, is classed as “Unable to Judge”, “Definitely Unrelated”, “Possibly Unrelated”, “Possibly Related”, “Probably Related”, “Definitely Related” (increasing severity of relationship).

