### **18.2.1 All Adverse Events**

The following AE summaries will be described frequency and percentage by treatment group and overall in an overview summary table:

- TEAEs
- Severity of AE (mild, moderate, severe)
- Treatment-Related AE
- Procedure-Realated AE
- Serious AEs
- Treatment-Related SAE
- Deaths
- AEs leading to withdraw from the study
- Treatment-Related AEs leading to withdrawal
- TEAE in  $\geq 5\%$  of patients
- Treatment-Related TEAE in  $\geq 5\%$  of patients

If a patient experienced more than one adverse event, the AE with the worst severity will be used in the corresponding summaries.

In addition, all AEs will be listed and presented by System Organ Class (SOC) and Preferred Term (PT) and also broken down further by maximum severity of event. If a patient reports an AE more than once within that SOC/ PT, the AE with the worst severity will be used in the corresponding severity summaries.

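### The SAP's procedure-relationship rule for repeat AEs selects on an undefined 'study medication', and it has no rule for a missing procedure relationship

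*SAP*

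**What the plan says.** Protocol 13.1.2 asks investigators to use the severity and causality tables when "determining relationship of the AE or SAE to the study device and procedure", so each AE has two attributions.

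SAP 18.2 handles the two in separate paragraphs.

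- **Device.** An AE is treatment-related if rated possibly, probably or definitely related, or unable to judge. On missing values: "AEs with a missing relationship to study treatment will be regarded as" definitely related. On repeats: "If a patient reports the same AE more than once within that SOC/ PT, the AE with the worst-case relationship to study medication" is the one used.
- **Procedure.** "AEs related to study procedure is defined as a AE with a relationship to the study procedure as" one of the same four categories. On repeats, "the AE with the worst-case relationship to study medication will be used in the corresponding relationship summaries". Nothing is said about a missing rating.

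The preceding paragraph lists the six categories in order of "increasing severity of relationship", with 'Unable to Judge' first and therefore lowest. SAP 8.1, after describing imputation of the primary reduction ratios, adds: "No additional data will be imputed". SAP 18.2.1 includes "Procedure-Realated AE" as a row of the overview table, by treatment group and overall.

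**The concern.** The procedure paragraph defines its event on one variable and chooses among repeat records on another. If the two ratings differ between records, the record kept for the procedure summary can be one that is not procedure-related while a qualifying record is set aside.

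The missing-value gap is a second, separate matter and needs no repeat event. SAP 18.2 counts missing severity as severe and a missing device relationship as definitely related. Of these three AE attributes, only the procedure relationship has no conservative rule.

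What is at stake is the accuracy of a safety row reported by arm, in a trial whose arms use different dialysis modes (HD and HDF). No efficacy endpoint depends on it.

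**Working it through.** The plan gives no figure to reproduce, so the check is of the text, followed by a count of logical combinations.

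**1. The three AE attributes side by side (SAP 18.2)**

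| Attribute | Repeat events: select on | Missing value |
|---|---|---|
| Severity | worst severity | severe |
| Device relationship | worst relationship to 'study medication' | definitely related |
| Procedure relationship | worst relationship to 'study medication' | no rule |

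The medication wording is the same in both relationship paragraphs, and Appendix 1 also speaks of a 'study med' start date. This points to carry-over from a drug-trial template.

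**2. One worked case.** A patient has the same PT twice.

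- Record A: device probably related, procedure definitely unrelated.
- Record B: device definitely unrelated, procedure probably related.

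If 'study medication' is taken to mean the device, A is kept. A table built on the kept record shows the patient as not procedure-related for that PT, although B meets the definition.

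**3. How often the logic fails.** Give each record one of 6 device and one of 6 procedure ratings: 6 × 6 = 36 record types and 36 × 36 = 1,296 ordered pairs. Four procedure categories count as related (24 record types) and two do not (12).

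- Pairs with at least one procedure-related record: 1,296 − 12 × 12 = 1,152.
- Pairs with exactly one: 2 × 24 × 12 = 576.
- Selecting on the device rating: the two device ratings tie in 576/6 = 96 pairs, where the rule does not decide. Of the other 480, half keep the wrong record: 240 lost.
- Selecting on the procedure rating in the SAP's stated order: the qualifying record is still lost when it is 'Unable to Judge' (6 record types) and the other is unrelated (12): 2 × 6 × 12 = 144 lost.
- Selecting on the procedure rating with 'Unable to Judge' ranked above the unrelated categories: 0 lost.

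These are counts of possible combinations, not expected frequencies. They show that replacing the word 'medication' is not enough by itself.

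**4. Missing rating.** A blank procedure relationship is none of the four listed categories. With no specific rule and nothing further imputed under SAP 8.1, such an AE would not qualify as procedure-related. The same AE with a blank device relationship would count as treatment-related.

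**5. Size.** One patient missed is 1/136 = 0.74% of an arm, two are 1.47% and three are 2.21%, assuming all 136 patients in the arm are treated.

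**The case against.** A reader might infer that procedure-related AEs will be lost from the overview count. The documents do not establish this. The repeat-event rule works within SOC/PT, and SAP 18.2.2 to 18.2.9 name no SOC/PT table of procedure-related events. The only procedure output named in the text is the overview row, which is not split by SOC/PT. If a patient is counted there whenever any AE meets the definition, Record B counts and nothing is lost. SAP 9 also gives the output templates priority over the text, and they are not available here.

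A reader might also infer that the SAP treats missing device and missing procedure ratings in opposite ways. It does not state a contrary rule for procedure; it states none. That the AE would go uncounted follows from the definition together with SAP 8.1.

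Nor do the documents define 'study procedure' as HD versus HDF, so the row cannot simply be read as a contrast between dialysis modes. Protocol 8.7.1.3 asks only for a summary by relationship to the study dialyzer.

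Exposure is limited as well. Protocol 13.1.2 requires a causal relationship for every AE, Protocol 9.5 and 9.11 provide for queries to be answered before lock, and all AEs are listed. A sensible programmer might read 'study medication' under a procedure heading as 'study procedure'.

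All of this stands as a limit on consequence. It does not make the rule correct as written: the term has no referent in this trial, the charitable reading still loses 'Unable to Judge' records under the stated ranking, and no reading of that term supplies the missing-value rule.

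**Conclusion.** The procedure-relationship rule is defective as written in two respects: an undefined selection variable that is not the procedure, and no provision for a missing rating. The ranking of 'Unable to Judge' compounds the first, because it conflicts with the definitions that count that category as related.

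A loss through record selection requires all of the following: a repeated PT in one patient, device and procedure ratings that disagree across the records, and a summary built from one record per SOC/PT. With a single study session and AE review at the next session, this should be uncommon. The missing-value gap reaches the overview row however repeats are handled, but only if a blank rating survives data cleaning. The number of such cases cannot be derived from the documents. It is probably very small, at about 0.7% of an arm per patient. This is a minor correction worth making before database lock.

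**What to change.** Edit SAP 18.2 as follows.

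- **Procedure paragraph:** select the repeat record on the worst relationship to the study procedure. Add that a missing relationship to study procedure is regarded as definitely related, as the device paragraph does.
- **Device paragraph:** replace 'study medication' with 'study device'.
- **Category order:** rank 'Unable to Judge' above the two unrelated categories, so that worst-case selection agrees with both definitions.
- **Overview row (18.2.1):** state that a patient is counted if any AE qualifies, and make the template match.

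The cost is a few sentences and no new data. The only downside is that the procedure-related count may be slightly higher.

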### **18.2.1 All Adverse Events**

The following AE summaries will be described frequency and percentage by treatment group and overall in an overview summary table:

- TEAEs
- Severity of AE (mild, moderate, severe)
- Treatment-Related AE
- Procedure-Realated AE
- Serious AEs
- Treatment-Related SAE
- Deaths
- AEs leading to withdraw from the study
- Treatment-Related AEs leading to withdrawal
- TEAE in  $\geq 5\%$  of patients
- Treatment-Related TEAE in  $\geq 5\%$  of patients

If a patient experienced more than one adverse event, the AE with the worst severity will be used in the corresponding summaries.

In addition, all AEs will be listed and presented by System Organ Class (SOC) and Preferred Term (PT) and also broken down further by maximum severity of event. If a patient reports an AE more than once within that SOC/ PT, the AE with the worst severity will be used in the corresponding severity summaries.

### **18.2.2 Adverse Events Leading to Withdraw From The Study**

AEs leading enrolled patients removed or withdraw from the study will be listed and summaries by SOC and PT.

### **18.2.3 Treatment-Related Adverse Events Leading to Withdraw From The Study**

Treatment-Related TEAEs leading enrolled patients removed or withdraw from the study will be listed and summaries by SOC and PT.

### **18.2.4 The Most Common ( $\geq 5\%$ Incidence) Adverse Events**

The most common(which total incidence is  $\geq 5\%$  or incidence of either treatment group is  $\geq 5\%$  ) adverse events will be listed and presented by SOC, PT and severity.

### **18.2.5 The Most Common ( $\geq 5\%$ Incidence) Treatment-Related Adverse Events**

The most common(which total incidence is  $\geq 5\%$  or incidence of either treatment group is  $\geq 5\%$  ) treatment-related adverse events will be listed and presented by SOC, PT and severity.

### **18.2.6 Serious Adverse Events**

Serious adverse events (SAEs) are those events recorded as ‘yes’ in “Serious” item on the Adverse Events page of the CRF. A listing and summary of SAEs by SOC and PT will be prepared.

### **18.2.7 Treatment-Related Serious Adverse Events**

A listing and summary of treatment-related SAEs by SOC and PT will be prepared.

### **18.2.8 Adverse Events Leading to Death**

AEs leading to Death are those events which are recorded as ‘Death’ on the Adverse Events page of the CRF. A listing and summary of AEs leading to death by SOC and PT will be prepared.

### **18.2.9 Treatment-Related Adverse Events Leading to Death**

A listing and summary of treatment-related AEs leading to death by SOC and PT will be prepared.

## **18.3 Device Deficiency**

Device deficiency, device deficiency resulted in an adverse event, and device deficiency resulted in a serious adverse event will be listed separately.

The following Device deficiency summaries will be described frequency and percentage by treatment group and overall in an overview summary table:

- Device deficiency

- Device deficiency reported to Baxter as a product complaint
- Device deficiency resulted in AE
- Device deficiency resulted in SAE

Device deficiency, device deficiency resulted in an adverse event, and device deficiency resulted in a serious adverse event will be listed separately.

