Statistical Analysis	
Analysis of Secondary Endpoints:
 
Secondary endpoints will be evaluated as follows:
 
A t-test or Wilcoxon Rank-Sum test, as applicable, will be used to evaluate differences between treatment groups in <math>Kt/V_{urea}</math> and URR.
 
A t-test or Wilcoxon Rank-Sum test, as applicable, will be used to evaluate differences between treatment groups for the RRs of <math>\alpha</math>1-MG, YKL-40, CFD, myoglobin and <math>\kappa</math> FLC obtained at the mid-week treatment day dialysis session.
 
Analysis of Safety Endpoints:
 
Safety endpoints will be evaluated as follows:
 
The summary of AEs will include AEs that occur on the day of or after the study treatment. Pre-treatment AEs including AEs reported at Screening and Randomization will be recorded in the eCRF but will not be summarized in the safety tables. Adverse events will be mapped to a Primary SOC and Preferred Term (PT) according to Medical Dictionary for Regulatory Activities (MedDRA) and summarized descriptively by SOC, PT and treatment group. Treatment group comparability in the incidence of AEs will be evaluated using Fisher's exact test.
 
Investigational device related product defects will be summarized descriptively. Comparator related product defects will not be collected or analyzed by Baxter.
 
Serum chemistry, hematology assessments, patient vital signs and CRP will be

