### **7.1.7. Safety Assessments**

- 1) AEs and SAEs;
- 2) CRP analysis;
- 3) Routine serum chemistry and hematology assessments;
- 4) Vital signs pre- and post-dialysis per treatment.
- 5) Device deficiencies (DDs) (during use of the investigational product; which would include functional characteristics [e.g., leaks, tubing separations, etc.])

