### 8.7.1.3 Analysis of Safety Endpoints

Safety endpoints will be evaluated as follows:

1. The summary of AEs will include AEs that occur on the day of or after the study treatment. Pre-treatment AEs including AEs reported at Screening and Randomization will be recorded in the eCRF but will not be summarized in the safety tables. Adverse events will be mapped to a Primary System Organ Class (SOC) and Preferred Term (PT) according to Medical Dictionary for Regulatory Activities (MedDRA) and summarized descriptively by SOC, PT and treatment group. Treatment group comparability in the incidence of AEs will be evaluated using Fisher's exact test. An overview (overall) summary table of all AEs will be generated that includes the total number of AEs, number and percentage of patients with at least one AE, number and percentage of patients with at least one SAE, number and percentage of patients with at least one severe AE, number and percentage of patients with at least one AE probably associated with study treatment, number and percentage of patients with an AE leading to study discontinuation and number and percentage of patients with an AE leading to death. This summary will be presented by treatment group and combining both groups (Total). In addition, two separate AE summary tables will be provided, one for analysis by severity and relationship to the study dialyzer, and the other will provide a separate AE summary table for SAEs and AEs that led to withdrawal from the study.
2. Device deficiencies (DD) will be summarized descriptively.
3. Serum chemistry, hematology assessments, liver function, patient vital signs, and CRP will be summarized descriptively per measurement time point using n, mean, median, standard deviation, minimum, and maximum.

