**Table 3. Causality Assessment \***

	treatment methods. The AE is resolved when the disease status is improved or other treatment methods are stopped. The AE occurs when other treatment methods are reused.	
Unable to Judge	It cannot be assessed with the above rationale.	YES

\*Causality assessment based on the Chinese medical device GCP

Causality: Performed by a medical professional and is a determination of whether there is a reasonable possibility that a medical device/procedure is etiologically related to/associated with an AE. Causality assessment includes, for example, assessment of temporal relationships, underlying disease, presence (or absence) of a more likely cause, and physiologic plausibility. Investigator shall provide an alternative etiology for SAEs that are definitely unrelated or possibly unrelated to use of study medical device. If the alternative etiology is unknown, investigator shall document “unknown.”

For AEs with causal relationship (Definitely Related, Probably Related, Possibly Related or Unable to Judge) to Theranova 400, the AE must also be reported as a device deficiency to the Sponsor.

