## **13.2 Product Complaints**

A Product Complaint (PC) includes any written, electronic, or oral communication that alleges deficiencies related to the identity, quality, durability, reliability, usability, safety, effectiveness, or performance of a product after it is released for distribution or related to a service that affects the performance of such product. A complaint may involve the possible failure of the product itself, its packaging, or its labeling (i.e., product label, package insert, or any instructions for use).

Reports of off-label use (in the absence of a device allegation or associated AE) are considered use error and need to be reported as complaints.

When a product complaint is encountered with a Post-Marketed Baxter product, the information should be reported to Baxter by the investigator to [REDACTED] within 24 hours of awareness of the event using the Product Complaint form. This should also include AEs with a positive causal relationship to a Post-Marketed Baxter device.

When a DD for the pre-marketed investigational device (Theranova dialyzer) is encountered, the information should be reported on the DD eCRF form and analysed by Baxter PMS (via [REDACTED] [REDACTED]). Product complaints reported for the comparator product will be collected based on each study site's established PC reporting processes and sent to the product manufacturer. Baxter will not analyze comparator-related PCs.

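### SAP 18.3 tabulates device deficiencies by arm and overall, but the protocol does not ascertain them by the same rules in both arms

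*SAP*

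**What the plan says.** **The planned table.** SAP 18.3: "The following Device deficiency summaries will be described frequency and percentage by treatment group and overall in an overview summary table". There are four rows: any deficiency, "Device deficiency reported to Baxter as a product complaint", deficiency resulting in an adverse event (AE), and deficiency resulting in a serious AE. Listings accompany the table. No test is planned.

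**Protocol text limited to the investigational device.** The Synopsis, under the safety analysis, plans a summary of defects of the investigational device and adds: "Comparator related product defects will not be collected or analyzed by Baxter". Protocol 7.1.7 scopes the assessment as "Device deficiencies (DDs) (during use of the investigational product; which would include functional characteristics"; the Synopsis safety list and 7.1.7.2.1 use the same scope. Protocol 13.2 says: "When a DD for the pre-marketed investigational device (Theranova dialyzer) is encountered, the information should be reported on the DD eCRF form". For the comparator, 13.2 has complaints collected under each site's "established PC reporting processes and sent to the product manufacturer".

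**Protocol text without limit by arm.** Protocol 8.7.1.3 says: "Device deficiencies (DD) will be summarized descriptively". Table 1 (13.1.1) defines a deficiency for medical devices in general. Sections 13.1.2 and 13.1.2.1 require every deficiency to be documented, each on its own form. The Schedule of Events (7.2.1.1) and the treatment visit (7.2.1.3) list deficiencies at the visit shared by both arms, and footnote 11 of the schedule has complaints recorded along with them.

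**A filing rule for one arm.** Below Table 3, for AEs with a causal relationship "to Theranova 400, the AE must also be reported as a device deficiency to the Sponsor". The Unable to Judge category counts as causal.

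**The concern.** A by-arm percentage invites comparison, and an overall percentage invites reading as the rate in the whole trial. Both need the same event to be looked for, and counted, in the same way in each arm. Here the two devices appear to be under different reporting rules, so a difference in the table could come from those rules and not from device performance. Deficiencies are a listed safety assessment, and the report is meant to support a registration application. Both mechanisms would make Theranova look worse than the FX 800, so the sponsor also has an interest in correcting them.

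**Working it through.** No figure in the plan needs to be reproduced. The check compares the passages and adds simple algebra.

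**Step 1. Is control capture settled?**

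| Points to Theranova only | Not limited by arm |
|---|---|
| Synopsis: comparator defects not collected or analysed by the sponsor | 8.7.1.3: deficiencies summarised, no arm named |
| Synopsis, 7.1.7, 7.1.7.2.1: scope is use of the investigational product | Table 1: definition covers medical devices generally |
| 13.2: deficiency form named for Theranova | 13.1.2, 13.1.2.1: all deficiencies, each on its own form |
| 13.2: comparator complaints go to their manufacturer | 7.2.1.1 with footnote 11, and 7.2.1.3: recorded at the shared visit |

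Section 7.1.7.2.1 belongs partly in both columns: its scope is the investigational product, but it then says that all deficiencies in the treatment period are recorded. No section states that FX 800 deficiencies go on the deficiency form, and none excludes them from it. A site could follow either reading. SAP section 4 lists two changes from the protocol, and neither concerns deficiencies.

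**Step 2. If control deficiencies are not captured.** Assume that all 136 randomised patients per arm are treated and counted in the safety set, and let x Theranova patients have a deficiency.

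- Theranova: x/136
- FX 800: 0/136, by construction
- Overall: x/(136 + 136) = x/272 = ½ × (x/136)

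Two values of x, chosen only for illustration:

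| x | Theranova | FX 800 | Overall |
|---|---|---|---|
| 5 | 5/136 = 3.7% | 0 | 5/272 = 1.8% |
| 10 | 10/136 = 7.4% | 0 | 10/272 = 3.7% |

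The factor of one half does not depend on x. It depends only on equal numbers treated per arm.

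**Step 3. If control deficiencies are fully captured.** The filing rule under Table 3 still works in one arm. Let a be the number of Theranova patients whose only deficiency is a filing made under that rule. Counted by patient, the first row rises by a/136 for Theranova and by 0 for the FX 800, even when the true rates of deficiencies and related AEs are the same in both arms. If every such patient already has another deficiency, a = 0 and the rise is nil. The documents give no rate of related AEs and nothing on overlap, so a cannot be estimated.

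**Step 4. The complaint row.** Section 13.2 sends comparator complaints to their own manufacturer. Footnote 11 has complaints recorded with deficiencies but does not route comparator complaints to the sponsor. The row therefore has no stated route for the control arm under either reading.

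**The case against.** The strongest reply is that this is a scoping gap more than a contradiction. The Synopsis, 7.1.7 and 13.2 are consistent with one another, and the general wording of 13.1.2 and 13.1.2.1 can be read down to the investigational product. The Synopsis also speaks of defects and 13.2 of complaints, which need not be the same as deficiencies. This stands as far as it goes, but it does not rescue the table. If the narrow reading is right, the FX 800 and overall columns should not be there.

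A second reply is that comparative safety does not depend on this table. SAP 18.2 and 18.2.1 summarise related AEs with one definition in both arms, including Unable to Judge, and SAP 18.3 also provides listings. That is correct and limits the importance of the point. It does not separate the rule-driven filings within the 18.3 rows. Whether those filings also enter the row for deficiencies resulting in an AE depends on a case report form that is not available here.

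A third reply is that the table templates may already restrict or footnote the table. They were not supplied. The SAP also cites protocol V1.0 Amendment 1, while the protocol at hand is V1.1, so it cannot be checked whether the deficiency wording changed between them.

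A reader might infer that FX 800 deficiencies will certainly go unrecorded, or that the table is distorted by a known amount. The documents support neither: the unrestricted sections leave control capture open, and no event rates are given.

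**Conclusion.** The concern holds in a limited form. SAP 18.3 plans a between-arm and overall display that the protocol's ascertainment rules do not support. Without control capture, the control count is zero by construction and the overall percentage is half the Theranova percentage, assuming equal numbers treated. With full control capture, the Theranova-only filing rule can still raise that arm's rows, by an unknown amount that may be nil. The complaint row has no stated control route in either case.

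The severity is minor. The table is descriptive and untested. It would be wrong to infer that the non-inferiority conclusion is at risk: the primary and secondary efficacy analyses do not use deficiency data.

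**What to change.** 1. Reconcile the protocol on whether comparator deficiencies are captured: Synopsis (safety assessments and safety analysis), 7.1.7, 7.1.7.2.1, 7.2.1.1 with footnote 11, 7.2.1.3, 8.7.1.3, Table 1, 13.1.2, the text under Table 3, 13.1.2.1 and 13.2.
2. If they are not captured equivalently, report Theranova-treated patients only, with that number as denominator. Drop the overall column, and state in a footnote that comparator deficiencies were not collected.
3. If they are captured equivalently, keep the by-arm table. Put deficiencies that arise only from the filing rule under Table 3 on a separate line, and show the complaint row for Theranova only.
4. Make the table template agree, because SAP section 9 gives the template priority over the SAP text.
5. Rest the between-arm comparison of related AEs on SAP 18.2.

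The cost is SAP wording, a footnote or an extra line, a template check and a protocol clarification. No new data analysis or assay is needed. If the study has started, Protocol 14.3 requires Ethics Committee approval before a revised protocol is implemented, so the protocol part is more than an editorial step.
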